### **6.1.2 Open-label Extension Phase**

Patients who received at least 30 doses of study drug (either placebo or active) during the 12-week Double-blind Treatment Period and continue to meet other eligibility criteria will be eligible to receive open-label CR845 for an additional 52 weeks. The Open-label Extension Phase will be comprised of the Open-label Treatment Period and the Follow-up Period. The first visit and first dosing for the Open-label Extension Phase of the study will occur immediately on the day of the last visit of the Double-blind Treatment Period or up to 1 week following the Double-blind Treatment Period. Each patient will receive CR845 at a dose of 0.5 mcg/kg after each dialysis session, 3 times per week for up to 52 weeks, whether they had been previously administered placebo or CR845. Prescription dry body weight will be recorded at the start of and every 12 weeks during the Open-label Extension Phase; if there is a  $\pm 10\%$  or more change from the prescription dry body weight recorded at Screening, then the CR845 dose will be adjusted according to the newly recorded dry body weight.

Patients will complete the 5-D Itch Scale during Weeks 4, 8, 12, 24, 36, and 52 (preferably at the end of the specified weeks).

Clinical laboratory tests, vital signs, adverse events, and concomitant medications will be monitored throughout the Open-label Treatment Period. Blood samples for inflammatory biomarkers will be collected periodically until the End-of-Treatment or Early Termination Visit. An electrocardiogram will be performed at the End-of-Treatment or Early Termination Visit.

The number and reason(s) for missed dialysis and the use of antipruritic medications will be recorded throughout the Open-label Extension Phase.

The last dose of open-label study drug will be administered at the last dialysis visit in Week 52.

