### 6.2.1 Inclusion Criteria

To be eligible for inclusion into the Double-blind Phase of the study, a patient must meet the following criteria:

1. Willing and able to provide written informed consent prior to participating in this study;
2. Able to communicate clearly with the Investigator and staff, able to understand the study procedures, and able and willing to comply with the study requirements, including providing written responses to questionnaires;
3. Male or female between 18 and 85 years of age, inclusive;  
**Note:** Subjects in Korea must be male or female between 19 and 85 years of age, inclusive;
4. Has ESRD and has been on hemodialysis 3 times per week for at least 3 months prior to the start of screening;  
**Note 1:** Patients who require an occasional additional dialysis treatment to manage fluid overload or electrolyte excesses may be enrolled as long as it is anticipated that no more than 1 such treatment will be required in any given week and no more than 4 occasions during the 12-week double-blind period. Patients routinely on 4 dialyses a week will not be eligible.  
**Note 2:** Patients receiving in-home hemodialysis may participate as long as they have switched to in-center hemodialysis at least 2 weeks prior to screening and plan to remain on in-center hemodialysis for the duration of the study.  
**Note 3:** Patients receiving alternate dialysis modalities such as nocturnal dialysis will not be eligible.
5. If female, is not pregnant or nursing during any period of the study;

- 
6. If female:
    - a. Is surgically sterile; or
    - b. Has been amenorrhoeic for at least 1 year and is over the age of 55 years;  
or
    - c. Has a negative serum pregnancy test at screening and agrees to use acceptable contraceptive measures (eg, hormonal contraceptives, barrier with spermicide, intrauterine device, vasectomized partner, or abstinence) from the time of informed consent until 7 days after the last dose of study drug;
  7. If male, agrees not to donate sperm after the first dose of study drug until 7 days after the last dose of study drug, and agrees to use a condom with spermicide or abstain from heterosexual intercourse during the study until 7 days after the last dose of study drug. (Note: No restrictions are required for a vasectomized male provided his vasectomy was performed  $\geq 4$  months prior to screening);
  8. Has a prescription dry body weight between 40.0 and 135.0 kg, inclusive;

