  9. Has at least 2 single-pool Kt/V measurements  $\geq 1.2$ , or at least 2 urea reduction ratio measurements  $\geq 65\%$ , or 1 single-pool Kt/V measurement  $\geq 1.2$  and 1 urea reduction ratio measurement  $\geq 65\%$  on different dialysis days during the 3 months period prior to screening;
  10. Prior to randomization:
    - a. Has completed at least four out of eight Worst Itching Intensity Numeral Rating Scale (NRS) worksheets from the start of the 7-day Run-in Period up to and including the pre-randomization assessment on Day 1;
    - b. Has a mean baseline Worst Itching Intensity NRS score  $\geq 5$ , defined as the average of all non-missing scores reported from the start of the 7-day Run-in Period up to and including the pre-randomization assessment on Day 1.

**To be eligible for inclusion into the Open-label Extension Phase of the study, each patient will have to fulfill the additional following criteria at the time of entry into the Open-label Extension Phase:**

11. Has received at least 30 doses of the planned 36 doses of study drug during the Double-blind Phase of this study;
12. Has a prescription dry body weight  $\geq 40$  kg;
13. Continues to meet inclusion criteria 1 through 7.

---

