**Table 2. Schedule of Events: Double-blind Phase**

Study Procedures	Screening Period		Double-blind Treatment Period a						Double-blind End of Treatment b/ Early Termination	Follow-Up Period (for patients not participating in Open-label Extension Phase ONLY)
	Screening Visit	Run-in Period	Week 1			Weeks 2 to 12				
	Day -28 to Day -7	Day -7 to Day 1	M/Tu	W/Th	F/Sa	M/Tu	W/Th	F/Sa		
	-28 to -7	-7 to 1	1	3	5	8	10	12	85	85 to 95
						15	17	19		
						22	24	26		
						29 k	31	33		
						36	38	40		
						43	45	47		
						50	52	54		
						57 k	59	61		
						64	66	68		
						71 k	73	75		
						78	80	82		
Administrative procedures										
Informed consent	X									
Inclusion/exclusion criteria	X		X c							
Medical history/Prior Medications (including antipruritic medications)/Demographics	X	X c	X c							
Randomization			X							
Safety and efficacy evaluations										
Physical examination	X									
Prescription dry body weight	X									
Pre-dialysis 12-lead electrocardiogram	X d								X d	
Pre-dialysis vital signs	X		X e			X e			X e	X f
Hematology, serum chemistry (pre-dialysis) g	X		X						X	
Serum pregnancy (females of childbearing potential only)	X o								X	

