**Table 3. Schedule of Events: Open-label Extension Phase**

Study Procedures	Open-label Treatment Period a Up to 52 Weeks of Dosing						Follow-Up Period	
	Day 1 c	Week 4 a	Week 8 a	Week 12 a	Week 24 a	Week 36 a	First Dialysis of Week 53 b End of Treatment /Early Termination	7 - 10 days after End of Treatment/Early Termination
Administrative procedures								
Inclusion/exclusion criteria	X d							
Safety and other evaluations								
Physical examination	X							
Record prescription dry body weight e	X e	Record every 12 weeks e						
Pre-dialysis 12-lead electrocardiogram f							X	
Pre-dialysis vital signs g	X	X	X	X	X	X	X	X
Hematology, serum chemistry (pre-dialysis)				X	X		X	
Serum pregnancy test for women of childbearing potential only				X	X		X	
Record number of missed dialysis visits and reason(s), as applicable		Record on an ongoing basis						
IV administration of study drug	X h	Dose after each dialysis up to Week 52 included h						

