**Table 3. Schedule of Events: Open-label Extension Phase**

(Continued)

Study Procedures	Open-label Treatment Period a Up to 52 Weeks of Dosing						First Dialysis of Week 53 b End of Treatment /Early Termination	Follow-Up Period 7 - 10 days after End of Treatment/Early Termination
	Day 1 c	Week 4 a	Week 8 a	Week 12 a	Week 24 a	Week 36 a		
Safety and other evaluations								
5-D itch scale i		X	X	X	X	X	X	
Inflammatory biomarker samples j					X		X	
Adverse event monitoring	Record on an ongoing basis k →							
Concomitant medications (including antipruritic medications)	Record on an ongoing basis k →							

IV = intravenous

- Each visit during the Open-label Treatment Period will coincide with the patient’s normal dialysis treatments. The study visit may occur on any chosen dialysis day of a scheduled week as long as all assessments are completed during that visit. However, it is recommended to avoid the first dialysis day of the week. Patients who miss one of the scheduled study visit weeks (eg, Week 4) may complete the visit procedures for this visit at their next dialysis treatment as long as it is within 2 weeks of the originally scheduled visit date.
- The End-of-Treatment Visit will be the first dialysis visit following the last dose of study drug (ie, first dialysis on Week 53).
- Day 1 of the Open-label Extension Phase can occur immediately on the day of the last visit of the Double-blind Treatment Period or up to 1 week following the Double-blind Treatment Period.
- Prior to dosing on Day 1 of the Open-label Extension Phase, the inclusion/exclusion criteria will be confirmed.
- The prescription dry body weight will be captured from the dialysis prescription and will be recorded on Day 1 and every 12 weeks during the Open-label Treatment Period (during Weeks 12, 24, 36, and 48). If there is a ±10% or more change in prescription dry body weight compared to the dry body weight recorded at screening, then the CR845 dose will be adjusted according to the newly recorded dry body weight. The date of prescription dry body weight change will also be recorded.
- Electrocardiogram must be performed prior to the start of dialysis.

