**6.5.4.6 Clinical Laboratory Tests**

Blood samples for clinical laboratory tests including hematology, serum chemistry, and serum pregnancy will be taken prior to dialysis and will be analyzed by a central laboratory. The laboratory tests include the following:

Assessment	Parameters to be analysed
Serum Chemistry	Albumin, Alkaline Phosphatase, ALT/SGPT, AST/SGOT, Bilirubin (Total), BUN, Calcium, Chloride, Creatinine, Glucose, Phosphorus, Potassium, Sodium
Hematology	Basophil %, Basophil (Absolute), Eosinophil %, Eosinophil (Absolute), Hematocrit, Hemoglobin, Lymphocyte %, Lymphocyte (Absolute), MCH, MCHC, MCV, Monocyte %, Monocyte (Absolute), Neutrophil %, Neutrophil (Absolute), Platelet, RDW, Red Blood Cells, White Blood Cells
Serum Pregnancy (females of childbearing potential only)	Human chorionic gonadotropin (HCG)

Processing and shipment of central laboratory samples will be described in the Laboratory Manual.

---

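### Open-label CR845 may be given on Day 85 before that day's pregnancy result is known, so a former placebo patient's first active dose can rest on a result 84 to 91 days old

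*Protocol*

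**What the plan says.** **When open-label dosing starts.** Protocol Section 6.1.2 states that the first open-label visit and dose "will occur immediately on the day of the last visit of the Double-blind Treatment Period or up to 1 week following" the double-blind period. The last double-blind visit is Day 85, the first dialysis of Week 13 (Table 2). Study drug is given at the end of the dialysis session (Section 6.4.1).

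**When pregnancy is tested.** In Table 2 the row "Serum pregnancy (females of childbearing potential only" is marked at Screening and at End of Treatment/Early Termination, and nowhere between. In Table 3 the row "Serum pregnancy test for women of childbearing potential only" is blank on Day 1 and marked at Week 12, Week 24 and End of Treatment. Under Section 6.5.4.6, samples "will be taken prior to dialysis and will be analyzed by a central laboratory"; processing and shipment are left to the Laboratory Manual.

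**What gates entry.** A Table 3 note says: "Prior to dosing on Day 1 of the Open-label Extension Phase, the inclusion/exclusion criteria will be confirmed". Criterion 13 for open-label entry reads "Continues to meet inclusion criteria 1 through 7". Among those, criterion 5 is "If female, is not pregnant or nursing during any period of the study" and criterion 6c is "Has a negative serum pregnancy test at screening and agrees to use acceptable contraceptive measures".

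**The standard at double-blind entry.** Section 6.1.1.1 and Table 2 note o require the serum test no more than 7 days before the first study dose, and Section 6.2 requires every eligibility criterion to be met before randomization.

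**The concern.** At the start of the study the protocol asks for a recent negative test before any study drug is given. For half of the patients that first study drug is placebo. Their first CR845 dose comes at open-label entry, where no comparable rule is written. A sample is taken at the right visit, but its result is not made a condition of dosing.

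A site that follows the text exactly can draw the Day 85 sample, confirm eligibility against a criterion that refers to screening, and give CR845 a few hours later. If the result then comes back positive, Section 6.5.4.7 requires immediate discontinuation, but the exposure has already occurred. What is at stake is avoidable exposure of an early pregnancy to the study drug. No efficacy result is affected.

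**Working it through.** **Inputs**
- Pre-study test: *k* days before Day 1, with *k* from 0 to 7 (Section 6.1.1.1; Table 2 note o).
- Double-blind End-of-Treatment Visit: 12 × 7 + 1 = Day 85, which agrees with Table 2.
- Last scheduled double-blind dose: Day 82 (Table 2).
- Open-label entry window: Day 85 to Day 85 + 7 = Day 92 (Section 6.1.2).

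**Age of the last known result.** For a dose on Day *d* with the Day 85 result not yet reported, age = (*d* − 1) + *k*.

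| Dose | Calculation | Age of last known result |
|---|---|---|
| Day 82, last double-blind dose | 81 + 0 to 81 + 7 | 81 to 88 days |
| Day 85, earliest open-label dose | 84 + 0 to 84 + 7 | 84 to 91 days |
| Day 92, result still outstanding | 91 + 0 to 91 + 7 | 91 to 98 days |
| Day 85 to 92, Day 85 result required | *d* − 85 | 0 to 7 days |

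**Does anything require the newer result?**
- Table 3, Day 1: no pregnancy test is marked.
- Table 3 eligibility note: the criteria are confirmed before dosing, but no result is named.
- Criterion 13: carries criteria 1 to 7 forward.
- Criterion 5: excludes pregnancy but names no test and no date.
- Criterion 6c: names a test, but the one at screening, which the old result satisfies.

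No sentence elsewhere in the protocol makes the first open-label dose wait for the Day 85 result.

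**How many doses are at issue?** Continuing the thrice-weekly pattern, sessions fall on Days 85, 87, 89 and 92. If dosing starts on Day 85 and the result is reported before the Day 87, 89 or 92 session, then 1, 2 or 3 doses have been given without it.

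**What deferral would cost.** Starting on Day 87, 89 or 92 instead of Day 85 defers those same 1, 2 or 3 doses. The interval since the Day 82 dose becomes 87 − 82 = 5, 89 − 82 = 7 or 92 − 82 = 10 days, instead of 85 − 82 = 3. For patients who continue, Section 8.8.2 runs the double-blind adverse-event window to the first open-label dose, so that window lengthens by 2, 4 or 7 days.

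**The case against.** The best defence is that entry is already gated. The open-label criteria must be met at the time of entry, criterion 5 is among them, and confirmation precedes dosing. A current serum sample is scheduled at that same visit, and a sensible investigator would look at it. Hematology and chemistry also have no Day 1 mark in Table 3, so the Day 85 draw plausibly serves as the entry sample for all three. Turnaround may be governed by the Laboratory Manual. Contraception is mandatory, and suspected pregnancy must be reported at once.

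Much of this stands. It shows that a current sample exists and that the blank Day 1 cell alone proves little. It does not show that the result must be known before the dose. Contraception also applied at double-blind entry, and the protocol still asked for a test within 7 days there.

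The second objection is also sound. The 7-day rule covers the first study dose only and sets no re-test interval. The protocol's own monitoring is sparser: no test between the pre-study sample and Day 85, and in the extension none between Week 24 and the End-of-Treatment Visit, so late doses rest on a result about 52 − 24 = 28 weeks old. By that schedule a 12-week-old result is ordinary for a woman already taking CR845. The argument from first exposure remains for former placebo patients.

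**Conclusion.** The gap is real but narrow. The protocol permits CR845 on Day 85 without the result of that day's pregnancy sample. For a woman of childbearing potential coming from placebo, her first active dose can then rest on a result 84 to 91 days old. For women already on CR845, Day 85 differs from Day 82 by three days.

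This rests on one assumption: that the central laboratory does not report between the pre-dialysis draw and the end of the session. Turnaround is not stated. A same-day result would close the gap in practice, though the text would still not require it.

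Three stronger readings are tempting and not supported:
- *A large multiple of a 7-day limit is being breached.* That limit applies to the first study dose and is not a re-test interval. It is a fair comparison only for a first exposure to CR845.
- *Open-label entry has no current test or no pregnancy check.* A sample is drawn on Day 85 and criterion 5 is reconfirmed; what is missing is the link between the result and the dose.
- *A known number of women or pregnancies will be exposed.* The protocol gives neither the share of women of childbearing potential nor a pregnancy rate, so no count can be derived.

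This is a patient-safety and eligibility point worth correcting. It has no bearing on the primary endpoint, power or the efficacy analysis.

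**What to change.** For women of childbearing potential, add one sentence to criterion 13 and one to the Table 3 note on Day 1 eligibility: a negative result from the Day 85 serum sample must be available before the first open-label dose. The entry window of up to one week already in Section 6.1.2 gives room for this, and the sample is already scheduled, so no new procedure is needed.

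The cost is a possible deferral of one to three dialysis-session doses for this small subset, and a double-blind adverse-event window longer by 2 to 7 days in those patients. If the laboratory reports on the same day, nothing is deferred. The sponsor should confirm that turnaround fits within the week; if it does not, the entry window for these women would need to be longer.

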### **6.1.3 Follow-up Period**

[figure not shown]
A final safety Follow-up Visit will be conducted 7-10 days after the End-of-Treatment Visit of the Double-blind Treatment Period for patients not participating in the Open-label Extension Phase, after the End-of-Treatment Visit of the Open-label Extension

Phase, or after the Early Termination Visit during either the Double-blind Treatment Period or the Open-label Extension Phase.

Vital signs, adverse events, and concomitant medications will be monitored during the Follow-up Period.

The study schematic is shown in [Figure 1](#).

**Figure 1. CR845-CLIN3103 Study Schematic**

---

## 6.2 Selection of Study Population

Patients with ESRD receiving hemodialysis 3 times a week and experiencing moderate-to-severe pruritus will be considered for participation in this study.

A screening log of potential study candidates will be maintained at each study site.

Patients providing informed consent will be screened for inclusion in the study. All eligibility criteria must be met before a patient is randomized.

Rescreening will be considered on an individual patient basis and must first be approved by the Sponsor or designee. However, rescreening will not be permitted if a patient missed the entry criteria for itch intensity, ie mean NRS score < 5. A patient can only be rescreened once. Rescreening can only occur after at least two weeks from screening.

### 6.2.1 Inclusion Criteria

To be eligible for inclusion into the Double-blind Phase of the study, a patient must meet the following criteria:

1. Willing and able to provide written informed consent prior to participating in this study;
2. Able to communicate clearly with the Investigator and staff, able to understand the study procedures, and able and willing to comply with the study requirements, including providing written responses to questionnaires;
3. Male or female between 18 and 85 years of age, inclusive;  
**Note:** Subjects in Korea must be male or female between 19 and 85 years of age, inclusive;
4. Has ESRD and has been on hemodialysis 3 times per week for at least 3 months prior to the start of screening;  
**Note 1:** Patients who require an occasional additional dialysis treatment to manage fluid overload or electrolyte excesses may be enrolled as long as it is anticipated that no more than 1 such treatment will be required in any given week and no more than 4 occasions during the 12-week double-blind period. Patients routinely on 4 dialyses a week will not be eligible.  
**Note 2:** Patients receiving in-home hemodialysis may participate as long as they have switched to in-center hemodialysis at least 2 weeks prior to screening and plan to remain on in-center hemodialysis for the duration of the study.  
**Note 3:** Patients receiving alternate dialysis modalities such as nocturnal dialysis will not be eligible.
5. If female, is not pregnant or nursing during any period of the study;

- 
6. If female:
    - a. Is surgically sterile; or
    - b. Has been amenorrhoeic for at least 1 year and is over the age of 55 years;  
or
    - c. Has a negative serum pregnancy test at screening and agrees to use acceptable contraceptive measures (eg, hormonal contraceptives, barrier with spermicide, intrauterine device, vasectomized partner, or abstinence) from the time of informed consent until 7 days after the last dose of study drug;
  7. If male, agrees not to donate sperm after the first dose of study drug until 7 days after the last dose of study drug, and agrees to use a condom with spermicide or abstain from heterosexual intercourse during the study until 7 days after the last dose of study drug. (Note: No restrictions are required for a vasectomized male provided his vasectomy was performed  $\geq 4$  months prior to screening);
  8. Has a prescription dry body weight between 40.0 and 135.0 kg, inclusive;
  9. Has at least 2 single-pool Kt/V measurements  $\geq 1.2$ , or at least 2 urea reduction ratio measurements  $\geq 65\%$ , or 1 single-pool Kt/V measurement  $\geq 1.2$  and 1 urea reduction ratio measurement  $\geq 65\%$  on different dialysis days during the 3 months period prior to screening;
  10. Prior to randomization:
    - a. Has completed at least four out of eight Worst Itching Intensity Numeral Rating Scale (NRS) worksheets from the start of the 7-day Run-in Period up to and including the pre-randomization assessment on Day 1;
    - b. Has a mean baseline Worst Itching Intensity NRS score  $\geq 5$ , defined as the average of all non-missing scores reported from the start of the 7-day Run-in Period up to and including the pre-randomization assessment on Day 1.

**To be eligible for inclusion into the Open-label Extension Phase of the study, each patient will have to fulfill the additional following criteria at the time of entry into the Open-label Extension Phase:**

11. Has received at least 30 doses of the planned 36 doses of study drug during the Double-blind Phase of this study;
12. Has a prescription dry body weight  $\geq 40$  kg;
13. Continues to meet inclusion criteria 1 through 7.

---

